**Table 1: Study Objectives and Endpoints**

Objectives	Endpoints
Primary	
To assess the efficacy of INCB050465 in terms of ORR in participants with MZL that is relapsed or refractory after at least 1 systemic treatment regimen.	ORR defined as the percentage of participants with a CR or PR as determined by IRC assessment of response according to CT-based response criteria for lymphomas (Cheson et al 2014).
Secondary	
To assess DOR.	DOR defined as the time from first documented evidence of CR or PR until disease progression or death from any cause among participants who achieve an objective response, as determined by radiographic disease assessment provided by an IRC.
To assess CRR.	CRR defined as the percentage of participants with a CR as defined by response criteria for lymphomas (Cheson et al 2014), as determined by an IRC.
To assess PFS.	PFS defined as the time from the date of the first dose of study treatment until the earliest date of disease progression, as determined by radiographic disease assessment provided by an IRC, or death from any cause.
To assess OS.	OS defined as the time from the date of the first dose of study treatment until death from any cause.
To assess the best percentage change in target lesion size.	Best percentage change in target lesion size from baseline, where target lesion size is measured by the sum of the product of diameters of all target lesion sizes.
To characterize the safety and tolerability of INCB050465.	Safety measured by AEs, 12-lead ECGs, chemistry and hematology laboratory values, vital signs, and physical examinations.

### 3. STUDY DESIGN

This is a Phase 2, open-label study designed to evaluate the safety and efficacy of 2 INCB050465 treatment regimens in participants diagnosed with relapsed or refractory MZL (see [Figure 1](#)). The study was originally planned to enroll 2 Cohorts: Cohort 1, comprising 60 participants who had received prior ibrutinib, and Cohort 2, comprising 60 participants who had not received a prior BTK inhibitor. However, Cohort 1 was closed to further enrollment for feasibility reasons per Protocol Amendment (Version) 3. Participants enrolled in Cohort 1 and the first 60 participants in Cohort 2 will be further allocated to 1 of 2 study treatment regimens as follows:

[figure not shown]
- Treatment A: INCB050465 20 mg QD PO for 8 weeks followed by 20 mg QW PO.
  - Participants in Cohort 1 receiving Treatment A will be referred to as Cohort 1A.
  - Participants in Cohort 2 receiving Treatment A will be referred to as Cohort 2A.
- Treatment B: INCB050465 20 mg QD PO for 8 weeks followed by 2.5 mg QD PO.
  - Participants in Cohort 1 receiving Treatment B will be referred to as Cohort 1B.
  - Participants in Cohort 2 receiving Treatment B will be referred to as Cohort 2B.

An interim futility analysis is planned for Cohort 2 when 30 participants have been treated and evaluated for response or have permanently discontinued study treatment because of disease progression, withdrawal of consent, or death. Cohort 2 will be terminated for futility if  $\leq 10$  of the 30 participants responded (ie, CR or PR) based on assessments provided by an IRC; otherwise the study for Cohort 2 will continue.

An additional 30 participants will be enrolled into one of the two treatment regimens (A or B) being evaluated in this study to better understand the safety and efficacy of INCB050465. The treatment regimen will be selected after enrollment is completed for Cohort 2 (ie, 60 participants enrolled) and will be selected after evaluation of emerging safety and efficacy data from this and other monotherapy studies of INCB050465 in non-Hodgkin's lymphoma. Once a treatment regimen is selected, the non-selected treatment regimen will be closed to further enrollment. Participants receiving the non-selected treatment regimen may switch to the selected treatment regimen or remain on their current treatment regimen, provided the participant has not met study-treatment withdrawal criteria and there are no safety concerns for their current treatment regimen. There will be no re-baselining for participants who switch treatment regimens and all participants will continue to follow the same assessment schedule.

Participants will receive treatment until disease progression, death, unacceptable toxicity, or consent withdrawal. Participants will be evaluated for ORR by an IRC and followed for DOR, PFS, OS, and safety.

**Figure 1: Study Design**

### 3.1. Randomization

Not applicable.

### 3.2. Control of Type I Error

There will not be any statistical comparison between Cohort 1 and Cohort 2. Within each of the 2 cohorts, there will not be any statistical comparison between the 2 treatment regimens, and 2-sided 95% CIs will be reported for all analyses when appropriate.

Within each cohort, no adjustment for alpha-spending is considered, as there are no plans to stop the study early for overwhelming efficacy. An IDMC will be assembled to monitor safety data and study conduct on a regular and ongoing basis during the study. The IDMC will also be charged with evaluating interim futility results. See Section 10 for details regarding interim analyses conducted in this study.

### 3.3. Sample Size Considerations

Cohort 1 was closed to further enrollment with Protocol Amendment (Version) 3.

The study will enroll up to 90 participants into Cohort 2. If the true ORR is 60%, then there is approximately 90% or 96% probability of observing the lower bound of the 95% CI of ORR  $\geq 40\%$  with 60 or 90 participants, respectively.

### **3.4. Schedule of Assessments**

See Protocol Amendment 4 dated 23 DEC 2019 for a full description of all study procedures and assessment schedules for this study.

## **4. DATA HANDLING DEFINITIONS AND CONVENTIONS**

### **4.1. Scheduled Study Evaluations and Study Periods**

#### **4.1.1. Day 1**

Day 1 is the date that the first dose of study drug (INCB050465) is administered to the participants.

#### **4.1.2. Study Day**

If a visit/reporting date is on or after Day 1, then the study day at the visit/reporting date will be calculated as

$$\text{Day \#} = (\text{Visit/Reporting Date} - \text{Day 1 date} + 1).$$

If the visit/reporting date is before Day 1, then the study day at the visit/reporting date will be calculated as

$$\text{Day \#} = (\text{Visit/Reporting Date} - \text{Day 1 date}).$$

A study day of -1 indicates 1 day before Day 1.

#### **4.1.3. Baseline Value**

Baseline is the last nonmissing measurement obtained before the first administration of INCB050465, unless otherwise defined.

When scheduled assessments and unscheduled assessments occur on the same day and time of the assessment or time of first dose is not available, use the following convention to determine baseline:

- If both a scheduled and an unscheduled visit are available on the day of the first dose and the time is missing, use the scheduled assessment as baseline.
- If all scheduled assessments are missing on the day of the first dose and an unscheduled assessment is available, use the unscheduled assessment as baseline.

#### **4.1.4. Handling of Missing and Incomplete Data**

In general, values for missing data will not be imputed unless methods for handling missing data are specified in this section or relevant sections. The original reported dates collected on the eCRF should be used in all relevant listings. The following rules will be used for handling missing or partial dates for analyses requiring dates.

When calculating time since initial diagnosis of cancer, partial diagnosis date will be handled in the calculation as follows:

- If only the day is missing, then the first day of the month will be used.
- If both the month and day are missing, then 01 JAN will be used.
- Otherwise, the time since diagnosis will not be calculated.

When the date of the last dose is used in deriving variables such as duration of treatment or TEAE flag, missing or partial date of last dose will be handled in the calculation as follows:

- If only the day is missing, then the earlier date of the last day of the month or the date that the participant discontinued treatment will be used.
- If both the month and day are missing, then the earlier date of 31 DEC of the year or the date that the participant discontinued treatment will be used.
- Otherwise, the date that the participant discontinued treatment will be used as the date of the last dose.

When calculating DOR, PFS, and OS, a partial date of death will be handled in the calculation as follows:

- If mmyyyy for the last known alive date = mmyyyy for the death date, then the day after the last known alive date will be used.
- If mmyyyy for the last known alive date < mmyyyy for the death date, then the first day of the death month will be used.
- Otherwise, the partial death date will not be handled.

When calculating time to onset or duration of a TEAE, a partial or missing AE onset/end date will be handled in the calculation as follows:

- If only the day is missing, then the first day of the month or Day 1, whichever is later, will be used as the onset date; the earlier date of the last day of the month or the date that the participant discontinued study or died will be used as the end date.
- If both the month and day are missing, then 01 JAN or Day 1, whichever is later, will be used as the onset date; the earlier date of 31 DEC or the date that the participant discontinued study or died will be used as the end date.
- Otherwise, Day 1 will be used as the onset date, and the missing end date will not be handled.

## **4.2. Variable Definitions**

### **4.2.1. Body Mass Index**

BMI will be calculated as follows:

$$\text{BMI (kg/m}^2\text{)} = [\text{weight (kg)}] / [\text{height (m)}]^2.$$

#### **4.2.2. Prior and Concomitant Medication**

Prior medication is defined as any nonstudy medication started before the first dose of INCB050465.

Concomitant medication is defined as any nonstudy medication that is started accordingly:

- Before the date of first administration of INCB050465 and is ongoing throughout the study or ends on/after the date of first study drug administration.
- On/after the date of first administration of INCB050465 and is ongoing or ends during the course of study.

A prior medication could also be classified as "both prior and concomitant medication" if the end date is on or after first dose of INCB050465. In the listing, it will be indicated whether a medication is prior-only, concomitant-only, or both prior and concomitant medication.

For the purposes of analysis, all medications will be considered concomitant medications unless the medications can unequivocally be defined as not concomitant.

## **5. STATISTICAL METHODOLOGY**

### **5.1. General Methodology**

Unless otherwise noted, SAS® software (SAS Institute Inc, Cary, NC; Version 9 or later) will be used for the generation of all tables, graphs, and statistical analyses. Descriptive summaries for continuous variables will include, but not be limited to, the number of observations, mean, standard deviation, median, minimum, and maximum. Descriptive summaries for categorical variables will include the number and percentage of participants in each category.

Interim analyses are planned for this study as defined in Section 10.

### **5.2. Treatment Groups**

This is a Phase 2, open-label study. All analyses will be conducted independently for Cohort 1 and Cohort 2, and there will not be multiplicity adjustment between the cohorts. Within each cohort, there will not be any statistical comparison between the treatment groups.

For the purpose of analysis, the 20 mg QW dosing period in Treatment A and the 2.5 mg QD dosing period in Treatment B are considered maintenance dosing periods. Within each cohort, data will be presented in summary tables by actual received treatment regimen and combined, with an exception for participants who cross over to the selected treatment regimen after the start of the maintenance dosing period.

For participants who cross over from the initially assigned treatment regimen to the selected treatment regimen, if the crossover happens before/on the start of the maintenance dosing period, then the participant will be summarized, according to the actual received treatment, in the selected treatment regimen; otherwise, the participant will be summarized in:

- A separate treatment regimen (ie, Crossover) for the safety summaries during the maintenance dosing period (eg. summaries of TEAEs and exposure).
- The initially assigned treatment regimen for all other summaries.

Per Protocol Amendment (Version) 3, Cohort 1 was closed to further enrollment. If the number of participants who have enrolled in Cohort 1 is relatively few, summary tables will be replaced with listings.

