• Any recurrent Grade 3 toxicity after 2 dose reductions.	Discontinue INCB050465 administration and follow-up per Protocol. Exceptions require approval of sponsor.
• Any other Grade 4 toxicity.	Discontinue INCB050465 administration and follow-up per Protocol. Exceptions require approval of sponsor.

ALT = alanine aminotransferase; AST = aspartate aminotransferase; CMV = cytomegalovirus; IV = intravenous; ULN = upper limit of normal.

Table 4: Dose Levels and Reductions for INCB050465

Timepoint	Treatment A	Treatment B
Starting dose	20 mg QD for 8 weeks (Day 1 through Day 56)	20 mg QD for 8 weeks (Day 1 through Day 56)
First dose reduction	10 mg QD	10 mg QD
Second dose reduction	5 mg QD	5 mg QD
Week 9 (Day 57) onward	20 mg once weekly ^a	2.5 mg QD ^b
First dose reduction	10 mg once weekly	1 mg QD ^c
Second dose reduction	5 mg once weekly	NA

^a All subjects will receive 20 mg once weekly at Week 9 (Day 57) regardless of prior dose level, unless a dose modification of a switch to a QW schedule before Week 9 is required for diarrhea/colitis management (see Table 5).

^b All subjects will receive 2.5 mg QD at Week 9 (Day 57) regardless of prior dose level, unless a dose modification of a switch to a QW schedule is required for diarrhea/colitis management (see Table 5).

^c Further dose modification due to diarrhea or colitis for subjects on 1 mg QD is permitted (see Table 5).

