
 • Diarrhea (≥ Grade 3). • Noninfectious colitis (any grade; confirmed or suspected). 	
Step 1: Interrupt INCB050465. Perform work-up for infection (including CMV, C. difficile, etc) immediately. Initiate or continue supportive care (see Section 5.4.2). Consider colonoscopy with biopsy for diarrhea ≥ Grade 3 and/or if symptoms^a suggestive of colitis. Monitor every 48 hours until resolution.
 
Step 2: If infection* is ruled out, start oral steroids, or consider IV steroids if participant is being given IV fluids. If no improvement with oral steroids within 48 hours, switch to IV steroids.
 
*For infectious diarrhea/colitis, follow institutional standard of care guidelines and restart parasclisib according to clinical judgement after resolved to ≤ Grade 1. Consult with medical monitor if needed.
 
Step 3: When diarrhea/colitis resolves to ≤ Grade 1, continue supportive care and taper steroids according to institutional standard of care. When taper is complete (eg, no steroid or ≤ 10 mg/day prednisone or equivalent) and diarrhea/colitis is ≤ Grade 1, restart INCB050465 as described herein and with approval of the medical monitor. Continue to monitor.
 
  
 INCB050465 Current Dose	Dose Modification	
   
 Any dose with QD dosing	20 mg QW regardless of Treatment A or B assignment	
 
 20 or 10 mg QW	Restart next lower dose	
 
 5 mg QW	Permanently discontinue	
  
 
Step 4: If ≥ Grade 3 diarrhea/colitis (any grade) reoccurs, permanently discontinue INCB050465.
	INCB050465 Current Dose	Dose Modification	Any dose with QD dosing	20 mg QW regardless of Treatment A or B assignment	20 or 10 mg QW	Restart next lower dose	5 mg QW	Permanently discontinue
INCB050465 Current Dose	Dose Modification								
Any dose with QD dosing	20 mg QW regardless of Treatment A or B assignment								
20 or 10 mg QW	Restart next lower dose								
5 mg QW	Permanently discontinue								

^a Diarrhea accompanied by abdominal pain and/or mucus or blood in stool.

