## 2. STUDY INFORMATION, OBJECTIVES, AND ENDPOINTS

### 2.1. Protocol and Case Report Form Version

This SAP is based on INCB 50465-204 Protocol Amendment 4 dated 23 DEC 2019 and CRFs approved 20 DEC 2018. Unless superseded by an amendment, this SAP will be effective for all subsequent Protocol amendments and CRF versions.

[figure not shown]

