## 6.4. Exposure

For participants in the safety population, exposure to INCB050465 will be summarized descriptively as the following:

- **Duration of treatment (days):** Date of last dose – date of first dose + 1.
- **Duration of treatment during the initial QD dosing period (days):** Date of last dose during the initial QD dosing period – date of first dose + 1.
- **Duration of treatment during the maintenance dosing period (days):** Date of last dose – date of first dose during the maintenance dosing period + 1. Crossover participants who switched to the selected treatment regimen after the start of the maintenance dosing period will be summarized in a separate group (ie, Crossover).
- **Average reported daily dose during the initial QD dosing period (mg/day):** total reported dose taken during the initial QD dosing period (mg) / duration of treatment during the initial QD dosing period (days).
- **Average reported daily dose during the maintenance dosing period (mg/day):** total reported dose taken during the maintenance dosing period (mg) / duration of treatment during the maintenance dosing period (days). Crossover participants who switched to the selected treatment regimen after the start of the maintenance dosing period will be summarized in a separate group (ie, Crossover).
- **Dose modifications:** Number of participants who had dose reduction and interruption will be summarized. The number of dose reductions and the number of interruptions for each participant will be summarized.

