- Summary of time to onset of selected TEAEs of special interest: life-table method
- Summary of longest duration of selected TEAEs of special interest

The following supporting summaries will be produced for TEAEs during the INCB050465 initial QD dosing period and the maintenance dosing period by MedDRA term. For the supporting summaries during the maintenance dosing period, participants who cross over to the selected treatment regimen after the start of the maintenance dosing period will be summarized in a separate group (ie, Crossover).

- Summary of TEAEs by PT in decreasing order of frequency
- Summary of TEAEs by PT and maximum severity in decreasing order of frequency
- Summary of Grade 3 or higher TEAEs by PT in decreasing order of frequency
- Summary of serious TEAEs by PT in descending order of frequency
- Summary of TEAEs with a fatal outcome by SOC and PT
- Summary of TEAEs leading to discontinuation of INCB050465 by SOC and PT

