- Section 9.2.2 was updated to include details of analyses on time to onset of selected TEAEs of special interest. Summaries of longest duration of selected TEAEs of special interest were added to have a better understanding of the safety profile in terms of duration of class-effect AEs as well as AEs influenced by treatment regimens. "Grade 2 or higher" was changed to "Grade 3 or higher" for time to onset summary of rash. This change was made to be consistent with other PI3K inhibitors, which highlighted more severe cutaneous reactions graded as Grade 3 or higher in the labeling. "Herpes simplex virus infection" was changed to "herpes simplex" based on MedDRA coding dictionary

as a broader term. Exfoliative dermatitis was added to the list of TEAEs of special interest.

- Section 9.2.3 was updated to include summary of TEAEs by PT and maximum severity in decreasing order of frequency, summary of longest duration of selected TEAEs of special interest, and additional supporting summaries during the INCB050465 initial QD dosing period and the maintenance dosing period, which will provide supportive data of the safety profile of the maintenance dose. Summary of nonserious of TEAEs by SOC and PT was removed because it will not be used for the clinical study report but will be provided for result disclosure.
- Section 9.3.2 was modified to include ALT and AST in the line graphs as additional supportive analyses for laboratory events of special interest.
- Section 9.3.3 was added to identify potential Hy's law events to better monitor liver toxicity.
- Section 9.3.4 was updated to align with the analysis plan for adverse events of special interest. Summary of worsening of laboratory events of special interest was removed because this is covered by the summary of worsening of laboratory abnormalities.
- Section 9.5 was updated to change the high threshold of QTcF and QTcB interval from 460 to 450 milliseconds for purpose of analysis. This change is to comply with the categories outlined in FDA Guidance for Industry (E14 Clinical Evaluation of QT/QTc Interval Prolongation and Proarrhythmic Potential for Non-Antiarrhythmic Drugs) used to characterize outliers in QTc values.

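### Does the SAP need a maintenance-period rule for Treatment B participants switched to weekly dosing before Week 9?

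*SAP*

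**What the plan says.** SAP 5.2 ties the maintenance period to regimen and dose: "the 20 mg QW dosing period in Treatment A and the 2.5 mg QD dosing period in Treatment B are considered maintenance dosing periods". It gives no calendar anchor such as Day 57. The same section groups participants by the regimen they actually received and has a special rule for those who cross over to the selected regimen. SAP 11.2 (Amendment 1) shows that the selected regimen is Treatment B.

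SAP 6.4 counts maintenance duration back from the last dose to the "date of first dose during the maintenance dosing period + 1". It ends the initial QD period at the last dose in that period. SAP 9.2.3 uses the same split: "The following supporting summaries will be produced for TEAEs during the INCB050465 initial QD dosing period and the maintenance dosing period by MedDRA term".

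In the Protocol, footnote b of Table 4 starts all Treatment B participants on 2.5 mg QD at Day 57, "unless a dose modification of a switch to a QW schedule is required for diarrhea/colitis management". Table 5 gives the restart for anyone on a QD dose as "20 mg QW regardless of Treatment A or B assignment".

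**The concern.** Take a Treatment B participant who has Grade 3 diarrhea in Week 4. Under Table 5 the drug is held and later restarted at 20 mg QW, and footnote b of Table 4 exempts this participant from 2.5 mg QD at Day 57. A period defined as the 2.5 mg QD period in Treatment B then never begins, and the SAP 6.4 formula has no start date to work from. A Treatment A participant with an identical dosing record does have one: the first 20 mg QW dose.

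The crossover rule does not help. It covers moves to the selected regimen, and here the participant moves away from the selected maintenance dose.

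At stake are the tables split by period, which SAP 11.2 says were added as something "which will provide supportive data of the safety profile of the maintenance dose". The affected participants would be those with diarrhea or colitis, which SAP 9.2.2 lists among the events of special interest. If two programmers chose differently, the same record could be split in two ways.

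**Working it through.** The plan states no figure on this point, so there is nothing to reproduce. The check compares the possible readings and puts a size on the difference.

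**Readings open to an analyst**

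1. Keep the participant in B and start maintenance at the first QW dose.
2. Keep the participant in B and start maintenance at Day 57.
3. Keep the participant in B but outside the maintenance tables, as for anyone who stops before Week 9.
4. Classify by regimen actually received, which puts the participant in A from the first QW dose.

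Reading 2 is weak. SAP 6.4 has no Day 57 anchor, and this reading puts QW doses into a period named for QD dosing.

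On readings 1 to 3, the event that prompts the switch is treated alike. It arises before the first QW dose, so none of them counts it under maintenance.

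**Exposure, readings 1 and 2**

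Inputs are the SAP 6.4 formulas and Day 57 from Table 4. Assumptions: 20 mg QD until the last QD dose, 52 weeks of treatment (Day 364), and a 14-day hold, which is the interruption that Protocol 5.4.1 allows before the sponsor must be contacted. QW doses then follow every 7 days, and the last falls on Day 358 in each case below.

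| Last QD dose | First QW dose | Duration from first QW dose (days) | Duration from Day 57 (days) | Difference (days) |
|---|---|---|---|---|
| Day 14 | Day 29 | 358 − 29 + 1 = 330 | 358 − 57 + 1 = 302 | 28 |
| Day 28 | Day 43 | 358 − 43 + 1 = 316 | 302 | 14 |
| Day 42 | Day 57 | 302 | 302 | 0 |

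With no hold at all the differences would be 42, 28 and 14 days. Table 5 rules that out, since it requires interruption and resolution to Grade 1 or lower before restart.

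The average dose in the initial period is 20.0 mg/day whenever that period ends at the last QD dose. It changes only if QW doses up to Week 8 are counted in it. The last such dose is on Day 50 in the first two cases:

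- Last QD dose Day 14: (14 × 20 + 4 × 20) / 50 = 7.2 mg/day.
- Last QD dose Day 28: (28 × 20 + 2 × 20) / 50 = 12.0 mg/day.
- Last QD dose Day 42: no QW dose before Day 57, so 20.0 mg/day.

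**Effect on a group mean**

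Assume 60 participants in B: half of the first 60 in Cohort 2 plus the additional 30. The documents do not give the allocation ratio. One affected participant then shifts

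- mean maintenance duration by at most 28 / 60 = 0.47 day;
- mean initial dose by at most (20.0 − 7.2) / 60 = 0.21 mg/day, and only on reading 2.

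**Adverse event percentages, reading 3**

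Leaving out one of N participants who had the event changes k/N to (k − 1)/(N − 1). The difference is (N − k) / [N(N − 1)], which is largest at k = 1, where it equals 1/N. If the participant did not have the event, the change is k / [N(N − 1)], again at most 1/N. For N = 60 that is 1.7 percentage points; for N = 30 it is 3.3.

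**How many participants**

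The number is not given. Protocol 5.4.4 says most immune-related events occur after the first 9 weeks. Appendix E indicates that QW switching for diarrhea and colitis came with Amendment 4 of 23 DEC 2019; the Amendment 2 entry had aimed to keep everyone on QD for the first 8 weeks. The study began in JUN 2017 with about 2 years of accrual planned (Protocol 1.4 and 4.5). On that timetable few or no participants would still have been in their first 8 weeks when the rule arrived. Actual accrual dates are not given.

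**The case for a change.** The best case for an amendment is that the SAP had its chance. It declares "This SAP is based on INCB 50465-204 Protocol Amendment 4 dated 23 DEC 2019", was amended in AUG 2020 and JAN 2021, and in the first of those revised the maintenance exposure formulas and added tables by period. Two sentences and one flag from existing dosing data would close the gap. In an open-label study it is tidier not to leave period assignment to programming.

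Part of this stands. No visible SAP text places these QW doses in a period, and the Protocol presents the switch as a dose modification within Treatment B, so reading 4 is not clearly intended.

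It does not carry an amendment, for three reasons. First, the dose labels in SAP 5.2 are evidently shorthand. Table 4 allows 10 mg and 5 mg QW in A and 1 mg QD in B from Week 9, and nobody would drop those reduced doses from maintenance because they are not literally 20 mg QW or 2.5 mg QD. Second, the obvious amendment, counting QW dosing as B maintenance, has its own cost: it mixes another schedule (20 / 7 = 2.86 mg/day on average) into tables meant to describe 2.5 mg QD. Leaving such participants out with a footnote may serve that purpose better, and reasonable statisticians would differ. Third, the SAP keeps sample displays and table shells in a separate document, which is the natural place for this level of detail.

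**Conclusion.** No change to the plan is needed. SAP 5.2 is silent on a narrow case that analysts can settle sensibly with a derivation note or a footnote. For one participant among an assumed 60 in B, the choice shifts mean maintenance duration by at most about 0.5 day and any maintenance-period percentage by at most about 1.7 points. These sizes assume a 14-day hold, a last QD dose between Day 14 and Day 42, and 52 weeks of treatment. They grow in proportion to the number of early switchers, which the documents do not give and which may be zero.

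Nothing inferential depends on the choice. The SAP makes no comparison between regimens. Pooled objective response rate, pooled secondary efficacy analyses and overall-period adverse event tables are identical under every reading. The individual records also remain visible in the planned dosing and adverse event listings (Listings 2.5.2 and 2.7.1).
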